Population	
Dyad Population
 
Total Sample: 345 Dyads (345 PWD + 345 caregivers)  Sample at NYU Site (VNAHG): 207  Sample at University of Utah Site (CNS; Central Utah): 86  Sample at University of Miami Site (FirstStat; Southern Florida): 52  Sample Description: PWD and their informal caregiver dyads. PWD must be 65 or older and informal caregiver 18 or over; English or Spanish speaking; Informal caregiver is defined as spending at least 8 hours per week and had an established prior relationship (family, friend, neighbor).

Study Sites	
NYU (lead): 0 clusters  VNAHG: 12 clusters  University of Utah: 5 clusters  University of Miami: 3 clusters

Number of participants	
Dyads: 345 across all sites (see population)

Description of Study Procedure	
The DSM-H is a multi-component quality improvement program that consists of clinician training, patient- and family-centered assessment instruments, patient-caregiver dyadic centered care plans, a BPSD assessment and treatment algorithm, and caregiver teaching sheets. This study will examine outcomes of this quality improvement program.

Reference Therapy	
Usual Care

Key Procedures	
None

Statistical Analysis	
Time trend analysis using repeated measure multivariate mixed effects linear models (PROC MCM in SAS) for all non-utilization outcomes. Utilization outcomes will be analyzed through logistic regression for odds of hospitalization or ER visit and Poisson Count regression for total number of hospitalizations and ER visits. Both will use random effects to measure for clustering.

CONFIDENTIAL

This material is the property of the NYU School of Medicine and Langone Medical Center. Do not disclose or use except as authorized in writing by the study sponsor

Interventional Template Version: 28 APR 2017

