### **4.2 Study Endpoints**

#### **4.2.1 Primary Study Endpoints**

Given that this is a dyadic, implementation science intervention, it is not appropriate to look at a single primary endpoint. There are therefore 3 primary endpoints that will be examined in this study. For the Aim 1 primary endpoint, PWD QOL, a 0.5 SD difference between the baseline and 60 day visit would be clinically meaningful based on prior studies and therefore considered a positive outcome. For the Aim 2 primary

CONFIDENTIAL

This material is the property of the NYU School of Medicine and Langone Medical Center. Do not disclose or use except as authorized in writing by the study sponsor  
 Interventional Template Version: 28 APR 2017

endpoint, informal caregiver QOL, given its rate of variability and floor and ceiling effects, a 0.5 SD difference between the baseline and 60 day visit would be clinically meaningful and therefore considered a positive outcome. For the Aim 3 primary endpoint, a 10% reduction in readmissions and ER visits at 60 days will be considered a clinically meaningful positive outcome. This would result in 220 fewer ER visits and 63.8 fewer admissions per 1000 patients based on prior evidence.

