## 10.4 Description of Statistical Methods

### 10.4.1 General Approach

Data Analysis will be performed using SAS 9.4. We will perform statistical tests to examine baseline differences between the quality improvement program and control groups. We will then perform unadjusted comparison of both primary outcomes (patient and caregiver quality of life, emergency room visits) and secondary outcomes (pain, BPSD, delirium, caregiver depression burden, and burnout, hospital and emergency room admissions) between groups. We will focus on the endpoint measure for quality of life, and 30 and 60-day outcomes for emergency room utilization. For primary and secondary outcomes, we will perform a time trend analysis using a mixed effects linear model (PROC MCM). Mixed effects regression is used to analyze longitudinal data with repeated measures accounting for intra-individual and group clustering. We intend to use multivariate mixed effects regression modeling as opposed to traditional linear modeling or ANOVA in order to control for unobservable confounding variables that are constant over time but differ across PWD and/or caregivers. For both primary and secondary outcomes, we will then repeat the above analyses adjusting for baseline variables as covariates for a more efficient measurement of the effects of the quality improvement program. We will also perform correlation analyses to explore the relationship between pain and BPSD, and PWD and caregiver QOL through plotting scores over time and then if a significant correlation is present through adding to our mixed effect model. For utilization data, we will perform logistic regression to examine whether the patient is more or less likely to have a hospitalization or ER visit compared when receiving the quality improvement program at 30 and 60 days. We will then perform a Poisson Count Regression to compare the total number of hospitalizations and ER visits at each timepoint. In these models we will utilize a random effect to measure for clustering.

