### 10.4.6 Additional Sub-Group Analyses

We will perform sub-group analyses based on age, sex, and race/ethnicity. We will perform both descriptive and multivariate comparisons.

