### 10.4.9 Exploratory Analyses

We will examine the effect of ADL function on non-QOL outcomes. We will also examine the interaction of caregiver and PWD primary and secondary outcomes.

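### The Aim 3 count model makes no provision for overdispersion between patients, so exploratory subgroup and ADL effects on ER visits and admissions could get standard errors that are too small

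*Combined protocol and SAP*

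**What the plan says.** Section 10.4.1 analyses utilization in two ways: logistic regression for any hospitalization or ER visit at 30 and 60 days, and a count model. On the second it says "We will then perform a Poisson Count Regression to compare the total number of hospitalizations and ER visits at each timepoint", and on the variance structure of both, "In these models we will utilize a random effect to measure for clustering". The Protocol Summary repeats this: "Poisson Count regression for total number of hospitalizations and ER visits", followed by "Both will use random effects to measure for clustering". Neither place names the level of the random effect. Since care teams are the randomized clusters, the care team is the natural reading.

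The documents contain no dispersion check, scale parameter, negative binomial alternative, robust standard error or patient-level term for the counts. Section 10.4.1 does mention clustering within individuals, but in describing the linear mixed models. Section 10.1 says that no formal SAP will be written, so no other document fills the gap.

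Two later sections plan analyses by patient characteristics. Section 10.4.6 says "We will perform sub-group analyses based on age, sex, and race/ethnicity", and section 10.4.9 says "We will examine the effect of ADL function on non-QOL outcomes". Utilization is a non-QOL outcome. Section 4.2.3 lists subgroup analysis among the exploratory endpoints.

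**The concern.** A Poisson model sets the variance of a patient's count equal to its mean, given the team and the covariates. For that to hold, all patients in a team with the same covariates must share one event rate. ER visits and admissions tend to recur in the same people, so the real variance is probably larger.

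A team random intercept can take up some of that extra variance, but only for a comparison made between teams. Sex, age, race/ethnicity and ADL function differ between patients in the same team. For those effects, and for their interaction with arm, the model would still use the Poisson variance. Intervals would be too narrow, and chance differences would be declared significant too often. Section 10.4.7 marks multiplicity as not applicable, so nothing else in the plan restrains such findings.

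**Working it through.** **Inputs from the documents.** Section 10.5 gives 20 care teams (10 per arm) of 15 completed dyads. Section 4.2.1 says "a 10% reduction in readmissions and ER visits at 60 days will be considered a clinically meaningful positive outcome" and equates this with 220 fewer ER visits and 63.8 fewer admissions per 1000 patients. The implied 60-day means are 220/0.10 = 2,200 and 63.8/0.10 = 638 per 1000, or 2.2 and 0.638 per patient. If 220 per 1000 were instead the base rate, the ER mean would be 0.22.

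**Assumptions.** The documents give no dispersion. Let φ be the ratio of variance to mean within a team. For negative binomial counts with mean μ, φ = 1 + kμ. The range considered for φ is 1.5 to 3. Team SD on the log scale is 0, 0.15 or 0.2.

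**The plan's own figure.** No power or precision is stated for the counts. The only figure is δ = .45 for the QOL outcome: SE = √(4 × (0.05 + 0.95/15)/20) = 0.1506, and with 18 df (2.101 + 0.862) × 0.1506 = 0.446. It reproduces. This confirms the 20 × 15 layout but says nothing about counts.

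**Effects within a team.** The team intercept cancels from a within-team contrast. Its true variance is φ times the Poisson variance, so model SE / true SE = 1/√φ, and the real error of a nominal 5% test is 2 × (1 − Φ(1.96/√φ)):

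| φ | SE ratio | Error, formula | Error, simulated arm-by-subgroup (team SD 0.15) |
|---|---|---|---|
| 1 | 1.00 | 5.0% | – |
| 1.5 | 0.82 | 11.0% | 10–11% |
| 2 | 0.71 | 16.6% | 14–18% |
| 3 | 0.58 | 25.8% | 23–24% |

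At a mean of 0.22, k = 0.5 gives φ = 1.11, SE ratio 0.95 and error 6.3%. With k = 2, φ = 1.44, the ratio is 0.83 and the error 10.2%.

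**The arm effect.** Arm is constant within a team. Overdispersion adds about (φ − 1)/(nμ) = k/n to the variance of a team's log mean, and the fitted team variance can rise to match. With k = 1, n = 15 and no true team effect, the fitted team SD should be near √(1/15) = 0.26. In simulation it was 0.23, and the SE ratio was 0.94 for arm but 0.59 for subgroup.

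**Simulation of the planned model.** 600 trials per row, Poisson with team intercept, team SD 0.2, all true effects zero. Entries are model SE / empirical SE and the z-test rejection rate; for arm, the rate with t on 18 df is added. The Monte Carlo standard error at 5% is √(0.05 × 0.95/600) = 0.9 percentage points.

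| Count, k (φ) | Subgroup | ADL | Arm × subgroup | Arm |
|---|---|---|---|---|
| ER, 0 (1.0) | 0.96, 6.8% | 1.02, 4.7% | 0.95, 6.2% | 0.93, 7.8%; t 5.5% |
| ER, 0.5 (2.1) | 0.74, 15.5% | 0.70, 17.8% | 0.68, 18.2% | 0.88, 8.8%; t 6.8% |
| ER, 1 (3.2) | 0.56, 27.2% | 0.55, 29.8% | 0.56, 28.5% | 0.96, 7.5%; t 5.2% |
| ER, 2 (5.4) | 0.42, 40.2% | 0.41, 43.8% | 0.43, 41.0% | 0.94, 7.5%; t 5.5% |
| Admissions, 0 (1.0) | 0.99, 4.3% | 1.00, 5.5% | 0.99, 4.5% | 0.94, 6.3%; t 4.7% |
| Admissions, 0.5 (1.3) | 0.88, 8.3% | 0.89, 9.3% | 0.83, 10.0% | 0.90, 9.2%; t 6.2% |
| Admissions, 1 (1.6) | 0.76, 13.7% | 0.79, 13.0% | 0.78, 12.5% | 0.97, 6.5%; t 5.0% |
| Admissions, 2 (2.3) | 0.64, 21.2% | 0.67, 18.2% | 0.67, 17.8% | 0.93, 8.5%; t 6.7% |

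The ER rows with k = 1 and 2 lie above the range of φ used for the conclusion.

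**The replacement.** At φ = 2 (1000 trials at each of the two means), a negative binomial model with the same team intercept brought arm-by-covariate errors from 17.2% and 14.4% down to 5.4% and 5.3%. Over all settings its error for within-team effects was 4% to 7%.

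**The case against.** The strongest reply is that H3 concerns only the arm contrast, which the random effect largely protects. That stands. A reader might infer that the main Aim 3 result is anti-conservative for this reason, but the arm column above does not support it. The small excess with z tests is also present at k = 0, and it mostly disappears with 18 df. The logistic models for any event have no separate variance to misstate, so they are not exposed.

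Second, sections 10.4.6 and 10.4.9 name neither the count model nor an interaction test, and both analyses are labelled exploratory (the first through section 4.2.3). This also stands in part. The Poisson model is the only count model in the plan, so its use there is the natural reading, but it is an inference. If subgroups were handled only by separate arm comparisons within each stratum, arm would again be constant within team and largely protected.

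Third, a reader might extend the point to covariate coefficients in the adjusted models, since section 10.4.1 says "we will then repeat the above analyses adjusting for baseline variables as covariates". The documents do not support that. The stated purpose of adjustment is a more efficient estimate of the program effect, no coefficient is put forward for interpretation, and the sentence precedes the utilization models.

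Fourth, the level of the random effect is not stated, and the summary uses the plural. If a patient-level effect was also intended for the counts, it would act as the missing overdispersion term. The text does not say so.

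Finally, the size rests on an assumed dispersion and on back-calculated means. It would therefore be wrong to say that the standard errors are too small as a matter of fact.

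**Conclusion.** The gap is real, conditional and minor. The plan fits Poisson counts with a random effect for clustering and allows for no further variation between patients. If there is such variation, and if the model is used for effects that differ within teams, their standard errors are too small. For φ from 1.5 to 3, false-positive rates are about 10% to 24% in simulation, with the formula slightly higher at the top of the range. At an ER mean of 0.22 they are about 6% to 10% for k from 0.5 to 2, and with no overdispersion the error is nil. The results at risk are exploratory. The Aim 3 arm comparison and the logistic models are not materially affected.

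**What to change.** In section 10.4.1 and the Protocol Summary, replace the Poisson model by a negative binomial model with the same random effect, and state that its level is the care team. A patient-level overdispersion term added to the Poisson model would also serve. In sections 10.4.6 and 10.4.9, say that any subgroup or ADL analysis of ER visit or admission counts uses this model.

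The cost is a sentence in each place, one extra parameter and slightly wider intervals. If the counts turn out to be close to Poisson, little is lost. The change is not meant to improve the arm test: at φ = 2 its z-test error was 9.3% and 6.9% at the two means with Poisson, and 8.1% and 4.7% with negative binomial.

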### 10.4.2 Safety Analyses

We will perform interim analyses using descriptive statistics and two-sided t-tests, monitoring for a significance of 0.05 starting at the end of year 1 of the grant for safety purposes. These results will be presented unblinded to the DSMB.

### 10.4.3 Adherence and Retention Analyses

We will perform sensitivity analyses to examine whether there are differences in those who are retained in the study vs those who withdraw/are terminated. As this is a cluster randomized trial, adherence is related to the quality improvement program implementation at the care team level and therefore falls under fidelity monitoring. We will examine differences in annual DSKA scores submitted by HHC clinicians across control and quality improvement program care teams through paired t-tests and repeated measures ANOVA.

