## **4 Study Design and Endpoints**

### **4.1 Description of Study Design**

This study will use a blinded cluster randomized controlled trial methodology. Each HHC care team will be randomized to either partake in the DSM-H performance improvement program or provide usual care. The project director based at NYU and RAs at all sites will be blinded to prevent bias in data collection. The study statistician based at NYU will perform the randomization utilizing SAS 9.4 stratified by agency and geographic location. The study PI will relay to the agencies which teams will serve as intervention or control. The study PI and statistician will not collect study data in order to maintain the integrity of the blinding. The potential for contamination between care teams randomized to receive the DSM-H performance improvement program and those who will provide usual care is minimal due to the nature of HHC clinician workflow where minimal time is spent in the office, and different care teams do not generally congregate with each other except during highly structured staff meetings. The investigators considered randomizing by site and using other HHC agencies; however, given the lack of contamination found in prior studies of the DSM-H combined with differences in care provision at other sites/locations and the need for a large number of clusters when using this methodology, the investigators felt this method was the most likely to provide valid and reliable results. It is not possible to randomize by patient in HHC because patients are seen by care teams in a given geographic region. Patients in the performance improvement group will receive care from a care team who has received the DSM-H performance improvement program, and those in the control will receive usual care from a care team who has not received the performance improvement program. Patients at the study sites are only cared for by members of the same care team and therefore there is no potential for patients to receive a mixture of care teams.

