### 6.1.6 Procedures for Training Quality Improvement Teams and Monitoring Fidelity

Because there are multiple care teams receiving the performance improvement program, and we need to understand how well the program is implemented in order to assess the research outcomes, we will measure fidelity of implementation (e.g. clinician exposure to the performance improvement program) as well as differences across control and performance improvement teams through assessing registered nurse, physical and occupational therapist knowledge, attitudes and confidence using Drs. [name] and [name]'s previously validated dementia symptom knowledge and attitudes survey at baseline, 6 months, and annually thereafter, comparing differences across intervention and control teams for contamination, and through measuring the number of care plans initiated, caregiver teaching sheets provided to caregivers, and assessment instruments used at each site and in each care team throughout the trial.

As the survey is primarily being collected for research purposes and not quality improvement purposes, we will consent clinicians who participate in the completion of the knowledge surveys. Completion of the training and clinical performance however will be seen as an operational, quality improvement requirement of the agencies, similar to Drs. [name] and [name]'s prior successfully IRB approved studies. Champions will hold a monthly conference call with the investigators and spend 4 additional hours each month performing performance improvement through PDSA methodology and Audit and Feedback and will receive guidance by the investigators to ensure adequate implementation, and are provided training in this during champions training. Additionally, as is standard practice with complex performance improvement programs we will hold annual site visits and include process-based interviews with managers and executive leadership to elicit suggested improvements, whether there have been any changes in usual care during the time, or any concerns that have not been previously addressed. Finally, we will collect OASIS data, which is a standardized nationwide clinical data set entered usually by the RN in HHC to examine difference between documentation and our gold standard assessments, as well as for performance improvement on a quarterly basis.

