#### **6.1.6.1.2.9 Withdrawal or Termination of Clinicians in Fidelity Monitoring**

Clinicians may choose to withdraw from the study at any point. They will be terminated from the study only if they leave the agency. We will continue to maintain enrollment even if clinicians miss a survey at a given time point and anticipate that not all clinicians will complete at all time points.

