## 10.6 Measures to Minimize Bias

### 10.6.1 Enrollment/Randomization/Masking Procedures

As randomization is done at the cluster (care team) level, this will only be performed at the beginning of the trial. The study statistician will perform the randomization utilizing SAS 9.4 stratified by agency. The PI will relay to the home care agencies which teams will serve as quality improvement program teams or control teams. The study RAs, study project director, and site-PIs will all be blinded to the assignment. Teams will be randomized in strata by agency and geographic location to ensure like care teams are assigned to each condition. Subjects will be assigned through usual practice to the care team that serves the geographic area they live in. We will sequentially recruit individuals as they are referred from agencies following the very clear, straightforward method described above in section [5.4](#).

Clinicians will be enrolled sequentially if they are eligible and all study personnel with the exception of the lead site PI and study statistician will be blinded as to the assignment of the clinicians within a performance improvement or usual care team.

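### The DSKA comparison between control and program teams names a paired t-test that cannot make it, and gives no team effect to either method

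*Combined protocol and SAP*

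**What the plan says.** Section 10.4.3 (Adherence and Retention Analyses) places adherence at the level of the care team. It then plans to examine differences in "annual DSKA scores submitted by HHC clinicians across control and quality improvement program care teams", and to do so "through paired t-tests and repeated measures ANOVA". Section 6.1.6 gives the purpose: the survey is used for "comparing differences across intervention and control teams for contamination".

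The design around it:

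- Section 4.1: "Each HHC care team will be randomized to either partake in the DSM-H performance improvement program or provide usual care". Each team is therefore in one arm only.
- Section 10.6.1: "Teams will be randomized in strata by agency and geographic location". Matched pairs are not described.
- Sections 6.1.6 and 6.1.6.1.2.7: the DSKA is taken at baseline, at six months and then yearly.
- Section 6.1.6.1.2.9: clinicians stay enrolled after a missed survey, and the investigators "anticipate that not all clinicians will complete at all time points".
- Section 10.4.1: mixed models that allow for repeated measures and clustering are planned for primary and secondary outcomes, and models with a cluster random effect for utilization. The DSKA is not listed under either.
- Section 10.5: intra-class correlation has to be controlled because randomisation is by cluster. The value used, .05, is stated for dyad outcomes.

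**The concern.** The contrast in 10.4.3 is between arms, while a paired t-test works on matched observations. The plan defines no match between a control clinician and a program clinician, or between teams across arms. Read literally, the analyst would have to invent pairs. Read as change within a clinician, the test no longer compares the arms.

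Repeated measures ANOVA can carry an arm factor, but the text mentions no team term. Clinicians in one team share champions, managers and workflow, so their scores are likely to be correlated. Ignoring that makes standard errors too small. In its classical form the ANOVA also keeps only clinicians with complete series.

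At stake is what the trial can say about implementation. A DSKA difference that looks real only because teams were ignored would give false reassurance that the arms stayed apart. Fidelity also feeds the safety reports (8.8.2) and is to be related to outcomes (10.3).

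**Working it through.** **Is there a pairing across arms?** Set side by side, 4.1 assigns whole teams to one arm and 10.6.1 describes strata, not pairs. The Protocol Summary lists 12 teams at VNAHG, "University of Utah: 5 clusters" and "University of Miami: 3 clusters". Odd counts of 5 and 3 cannot be fully paired within an agency. No cross-arm pairing is available, by clinician or by team. Pairs do exist within a clinician between waves.

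**Inputs for the size of the effect.** The documents give no sample size, power, alpha or ICC for the DSKA comparison, so there is no stated figure to reproduce.

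- Clinicians: 300 (6.1.6.1.1 and 10.5).
- Teams: 12 + 5 + 3 = 20, 10 per arm (Protocol Summary, 10.5).
- Clinicians per team: 300/20 = 15, if equal (assumption).
- ICC: .05 borrowed from the dyad calculation; .01 to .10 taken as a range (assumption).
- Two-sided alpha .05 (assumption for the DSKA).

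As a check that the cluster inputs are usable, dyad power was recomputed with a noncentral t on 18 degrees of freedom. The variance is 4 × (.05 + .95/15)/20 = .0227, the standard error .151, and the noncentrality .45/.151 = 2.99. Power is .807 against the stated .80.

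**Error of a single-wave arm comparison that ignores teams.** Design effect DE = 1 + (15 − 1) × ICC. True two-sided error = 2 × (1 − Φ(1.96/√DE)).

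| ICC | DE | Effective clinicians (300/DE) | True error |
|---|---|---|---|
| .01 | 1.14 | 263 | 6.6% |
| .02 | 1.28 | 234 | 8.3% |
| .05 | 1.70 | 176 | 13.3% |
| .10 | 2.40 | 125 | 20.6% |

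A simulation with no true effect (20,000 runs, 20 teams of 15) agrees. The unpaired test that ignores teams rejected in 6.8%, 13.0% and 20.9% of runs at ICC .01, .05 and .10. Pairing 150 against 150 clinicians arbitrarily gave nearly the same: 6.7%, 13.0% and 20.8%. A t-test on 10 against 10 team means held 5.0%, 4.5% and 5.0%.

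**If the paired test means change within an arm.** Assume both arms rise by 0.3 SD, with a correlation of 0.6 between waves, 150 clinicians per arm and no team effect. The control-arm paired test was then significant in 98.5% of 5,000 simulated trials, although the arms did not differ. Such a test says nothing about the arm contrast.

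**Loss under a complete-series analysis.** With independent response at rate r in each wave, the share completing k waves is r^k. The number of waves per clinician is not stated; four and five are shown.

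- r = .80 (assumption): .80⁴ = 41%; .80⁵ = 33%.
- r = .92, the lower figure for past recruitment and retention in 6.1.6.1.2.2, read here as a per-wave rate (assumption): .92⁴ = 72%; .92⁵ = 66%.
- r = 1.00, the upper figure there: no loss.

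**The case against.** The best defence is that the sentence names two methods which can be assigned sensible jobs: ANOVA with an arm factor for the arm-by-time contrast, and paired t-tests for each clinician's change. The data would support both, since the same clinicians are surveyed repeatedly. That much stands, and a reader should not infer that no pairs exist at all or that both methods are invalid. It does not rescue the text, which attaches both methods to the control-versus-program contrast and gives neither a team effect.

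Other stronger readings are tempting and are not supported:

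- **The test runs at 13%.** That is one point in a range. It rests on an ICC set for dyads and on equal teams, and it applies to a single-wave comparison. The error of an arm-by-time test depends on the team ICC of change, which the documents do not give.
- **Most clinicians would be lost.** This follows from 80% response, not from the protocol's own 92–100%. It also presumes a complete-case ANOVA, and the implementation is not stated.
- **A null quality-of-life result would be explained by this comparison.** No section says so. Section 6.1.6 also counts care plans, teaching sheets and instruments used, collects OASIS data, and holds annual site visits.
- **Control-arm change measures contamination.** It also reflects repeat testing and changes in usual care. The site-visit interviews in 6.1.6 ask about changes in usual care, and 6.1.6.1.2.8 looks for changes across the agency.
- **The six-month survey is deliberately left out.** Section 10.4.3 says annual, but 6.1.6 puts all waves beside the arm comparison, so this may be shorthand.

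**Conclusion.** The analysis in 10.4.3 is wrong as written, on two counts. A paired t-test cannot make a comparison between arms, and no team effect is stated for either method although the team is the randomised unit. The second count departs from the plan's own reasoning in 10.4.1 and 10.5.

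If teams are ignored, a nominal 5% comparison at one wave runs at about 7% to 21% for ICCs of .01 to .10, assuming 20 equal teams of 15. The inflation is above nominal throughout that range, but its size is uncertain because no DSKA ICC is given. The loss from complete-series analysis runs from none to more than half of clinicians over four waves, depending on response.

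The consequence is confined to what the trial concludes about fidelity and contamination. The DSKA is not a primary or secondary endpoint, and no efficacy analysis changes. The sentence should be corrected, but the trial's main conclusions do not depend on it.

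**What to change.** Replace the DSKA sentence in 10.4.3 with a single model:

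- a linear mixed model of DSKA score on arm, wave (baseline, six months, each annual survey) and arm-by-wave;
- random intercepts for clinician and for care team;
- the agency stratum as a covariate;
- small-sample degrees of freedom suited to 20 teams.

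This model makes the arm contrast at each wave, names the six-month survey explicitly, and uses clinicians with incomplete series. Keep paired tests, if at all, only to describe change within an arm. State that control-arm change is a possible signal of contamination, to be read together with the other fidelity data in 6.1.6.

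The cost is a sentence or two in 10.4.3. It needs no new data, and the SAS software already planned can fit the model.
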